9.9 Protocol Deviations

All the requirements in the trial protocol must be strictly followed. Any deviation from protocol and regulations in GCP will be defined as protocol deviation. If a deviation is identified, the deviation record should be filled in, and the time of occurrence, process, reason for deviation and measures taken, etc. should be recorded in detail, and the ethics committee and sponsor should be notified. In the data statistics and report, investigators will analyze the impact of deviations on the final data and conclusions.

When a serious protocol deviation occurs, an assessment should be made. If necessary, the sponsor can terminate this trial early.

10 GENERAL CONSIDERATIONS: REGULATORY, ETHICAL, AND TRIAL OVERSIGHT

10.1 Regulatory and Ethical Considerations

Consensus ethical principles derived from international guidelines including the Declaration of Helsinki, ICH GCP Guidelines and the local regulations where the trials will be conducted as well as other applicable laws and regulations issued by FDA where the trials will be submitted.

10.2 Committees

The trial must be approved by the Ethics Committee prior to the trial implement. The Principal Investigator and sponsor will provide the IRB/IEC with all requisite material, including the application form for ethical review, resume and qualification of PI, a sample informed consent form, protocol, CRF, Investigator brochure, recruiting materials, *etc.* Any protocol amendment must be approved by or filed to the Ethics Committee during the trial. It is the responsibility of the investigator to inform the Ethics Committee that the trial has been completed as per the relevant requirements.

10.3 Informed Consent Process

Participants must sign the written informed consent to protect their legal rights before any procedure. It's the investigators' responsibility to fully and comprehensively introduce trial objective, design, the drug effect, the expected benefit, the possible side/toxicity effects and risks to the participants. Investigators should promptly inform participants of any new information about the investigational products. Participants should be informed that the participation in the clinical trial is completely voluntary and they can withdraw from the trial at any time without any reason without punishment or loss of their rights due to withdrawal. Participants should be also informed that the investigators and sponsor have the right to read, save and statistically process their data in accordance with relevant regulations. Only participants who fully understand the risks / benefits and potential AEs, sign and date on the informed consent form can be enrolled in this trial. If the clinical protocol is modified during the trial, the informed consent form should be updated if necessary, and the participants' informed consent should be re-obtained after approval by the ethics committee.

10.4 Data Protection

All information generated in the trial will be kept strictly confidential and must not be disclosed to anyone not involved in the trial without the written permission from the sponsor.

Investigator should retain all study-related documents for the authority and sponsor

evaluation and audit, including: original medical records, informed consent forms, case report forms, the detailed distribution records of investigational drugs, *etc.* Files archived both in paper or electronic format should be traceable. The ethics committee should keep all records of ethics review, including written records of ethics review, member information, documents submitted, meeting minutes, and other related records, and all records should be kept for at least 5 years after the end of the clinical trial. The essential documents shall be retained at least 5 years after approval of marketing application or at least 5 years after the completion of the clinical trial (not for marketing application). All materials of this clinical trial are the property of sponsor, and the documents shall not be damaged without prior written agreement between the investigator and the sponsor. Notification to sponsor should be prior to any transference to another party or another place. Unless required by the regulatory authorities, the investigator shall not provide trial files to a third party in any form without the written consent of the sponsor.

10.5 Early Site Closure or Trial Termination

10.5.1 Termination Criteria

The trial will be terminated in the following conditions:

- 1) Refer to CTCAE 5.0, if more than half of the participants experience drug-related AEs of Grade 2, or more than a quarter of the participants experience drug-related AEs of Grade 3-4; or indication in which obvious intolerance;
- 2) Termination requested by the sponsor on the premise of full ensuring the legal rights and safety of participants;
- 3) Termination demanded by NMPA or Ethics Committee due to some reasons;
- 4) Other conditions in which the trial cannot be continued.

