	
degree of completion of the trial and withdrawal reasons. The relevant notes for data inclusion/exclusion should be recorded. Conditions in which data should be excluded can be as follows (not limited to):
 
 1) Data of participants who don't meet the inclusion criteria or meet the exclusion criteria, which may affect the results; 2) Data of participants who are incompliant with the clinical protocol during the trial, which should be judged rationally according to the severity of protocol deviations; 3) Data of participants with other behavior which may affect pharmacokinetics results during the trial; 4) After taking investigational product, the data of individual participants will be excluded from PK similarity analysis (PKSS) on condition that: 
 a. Participants who have positive results of ADA at baseline (0 h); b. The first postdose sample provides C_{max} values; c. The pre-dose (0 h) sample provides a quantifiable concentration value; d. Concomitant medication occur during the trial and there is clear evidence that the combination medication has an effect on the pharmacokinetics (PK) of the investigational products.
Termination Criteria	
 1) Refer to CTCAE 5.0, if more than half of the participants experience drug-related AEs of Grade 2, or more than a quarter of the participants experience drug-related AEs of Grade 3-4; or indication in which obvious intolerance; 2) Termination requested by the sponsor on the premise of full ensuring the legal rights and safety of participants; 3) Termination demanded by NMPA or Ethics Committee due to some reasons; 4) Other conditions in which the trial cannot be continued.
PK Evaluation	
The primary PK endpoints are the maximum serum drug concentration (C_{max}) and areas under the serum concentration versus time curve extrapolated to infinity ($AUC_{0-\infty}$).
 
The secondary pharmacokinetic endpoints are areas under the serum concentration versus time curve calculated to the last measurable observation (AUC_{0-t}) and to 65 days postdose ($AUC_{0-65\text{days}}$), the time to maximum serum concentration (observed) (T_{max}), the elimination half-life ($t_{1/2}$) and terminal elimination rate constant (K_{el}), apparent distribution volume (V_d/F) and clearance (CL/F).

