6.6 Participant Assignment, Randomization and Blinding

6.6.1 Participant Assignment

This is a single-center, randomized, single-blind, single-dose, parallel-group comparative pharmacokinetic trial in healthy adult participants.

There will be 238 healthy participants to be enrolled in the fasting trial and they will be randomized to one of two treatment groups (T, R), with an equal number of participants per treatment group.

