6.6.2 Randomization

During the screening period, the screening number will be assigned to identify participants (e.g., S001). The participants will be randomized on Day -1. The stratified block randomization will be adopted. Participant random No. will be "10XX". When the randomized participant withdraws from the trial, random No. will be retained and the participant won't be enrolled again regardless of the withdrawal reason and whether a treatment has been received.

The randomization schedule will be generated by statistical department (an unblinded statistician) using SAS (Version 9.4 or higher).

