6.6.3 Blinding and Unblinding

This is a single-blind trial. Only the designated clinical site personnel responsible for drug distribution and administration could reach the randomization code. The personnel and procedure should be blinded as following:

In course of the trial, sponsor staff, investigators in the clinical site and clinical research associates (other than those responsible for drug distribution and administration), statistician (other than unblinded statistician), data managers should be blinded to the treatment assignment. Staff who are responsible for drug distribution and administration

should not conduct any protocol-specified safety assessments, e.g. AE or injection site assessments post-dose.

The participants will be blinded to the assigned treatment (T or R) through the dosing process. An eye mask will be put on for participants to avoid viewing the injection.

In addition, the identity of the dosing drug will remain blinded to the bioanalytical staff during sample analysis.

Individual participant treatment assignment should be unblinded in the case of a suspected unexpected serious adverse reaction (SUSAR) that requires knowledge of the study medication received by the participant in order to interpret the event, may be essential for medical management of the participant, and may provide critical safety information about a drug that could have implications for the ongoing conduct of the trial. Otherwise unblinding is not allowed. Any blinding should be documented and dated. Treatment assignments for individual participants will remain blinded until after the study database has been cleaned and locked.

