7.4 Trial Stopping Rules

Not Applicable.

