9.7 Interim Analyses

Not Applicable.

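### The numeric termination rule uses separate grade bands, so Grade 3-4 events do not add to the Grade 2 limb and Grade 5 counts in neither: 60% of participants with Grade 2 or worse can fire neither limb

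*Protocol*

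**What the plan says.** Protocol 10.5.1 lists four grounds for terminating the trial. Item 1 refers to CTCAE 5.0 and has three triggers in one sentence: "more than half of the participants experience drug-related AEs of Grade 2, or more than a quarter of the participants experience drug-related AEs" of Grades 3-4, or an indication of obvious intolerance, which is not defined. The synopsis repeats the rule ("if more than half of the participants experience drug-related AEs of Grade 2", and so on). Items 2-4 cover termination by the sponsor, by NMPA or the Ethics Committee, and for any other reason that the trial cannot continue.

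The rule names no arm. It does not say whether the denominator is participants enrolled, dosed, or dosed so far, and it does not say when the count is made.

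Section 12.3 defines Grades 1 to 5, with Grade 5 being death related to an AE. Section 12.4 counts possibly related events as drug-related. Section 7.4, "Trial Stopping Rules", and Section 9.7, "Interim Analyses", are both marked not applicable. The SAP carries the grade scale (5.6.1) but no termination rule.

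**The concern.** A stopping rule should become more likely to fire as events become more severe. As written, this one can do the opposite. If a participant's only drug-related event is Grade 3 rather than Grade 2, that person drops out of the one-half limb and enters a limb that may be far from its own threshold. A drug-related death enters neither numeric limb.

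The rule protects healthy volunteers who are told to expect no benefit (Section 2.2). Non-serious Grade 2 events do not enter the SAE or SUSAR routes, so this limb is the only numeric check on them. At stake is whether the numeric part of the rule does what its readers will assume. The PK similarity analysis is not affected.

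**Working it through.** **Inputs.** 238 participants (Sections 6.6.1 and 9.8), 119 per group. Thresholds of more than one half and more than one quarter (10.5.1). The plan gives no operating characteristic for the rule, so there is no figure of its own to reproduce. The denominator 238 does reproduce: a CV of 44% gives a log-scale SD of sqrt(ln(1 + 0.44²)) = 0.4207; exact TOST power at 101 per group is 89.99%; and 202/0.85 = 237.6, rounded up to 238.

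**Thresholds in participants.** Grade 2 limb: 238/2 = 119, so 120 are needed. Grade 3-4 limb: 238/4 = 59.5, so 60 are needed.

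**The bands, read literally.** Each participant is classed by a single worst drug-related grade and has no other drug-related event of Grade 2 or above.

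| Grade 2 only | Grade 3-4 only | Grade 2 or worse | Rule as written | Cumulative wording |
|---|---|---|---|---|
| 120 (50.4%) | 0 | 120 (50.4%) | fires | fires |
| 119 (50.0%) | 1 (0.4%) | 120 (50.4%) | does not fire | fires |
| 95 (39.9%) | 48 (20.2%) | 143 (60.1%) | does not fire | fires |
| 119 (50.0%) | 59 (24.8%) | 178 (74.8%) | does not fire | fires |

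Rows one and two differ by one person, whose event is Grade 3-4 instead of Grade 2. The more severe outcome switches the rule off. Row three is an illustration (40% and 20% of 238, rounded). Row four is the most that can occur without a trigger: 119 + 59 = 178. A Grade 5 event adds nothing to either limb in any row.

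**False stops under cumulative wording, pooled count.** The documents set no count schedule. I assumed counts at 80 and 160 dosed, event outcomes known at each count, independent participants, the same rates in both arms, and 2% Grade 3-4. Let A be the number with Grade 2 only and B the number with Grade 3-4.

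- As written: fires if A ≥ 41 or B ≥ 21 at 80 dosed, or A ≥ 81 or B ≥ 41 at 160.
- Reworded: the same, with A + B in place of A.

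Exact calculation over both counts, excluding the Grade 5 trigger:

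| Assumed Grade 2 rate | As written | Reworded |
|---|---|---|
| 30% | 0.01% | 0.03% |
| 35% | 0.21% | 0.66% |
| 40% | 2.88% | 6.65% |

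Most of this arises at the first count. In the last row, P(Bin(80, 0.40) ≥ 41) = 2.71% and P(Bin(80, 0.42) ≥ 41) = 5.98%.

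**What the rewording gains.** If the true rates were those of row three of the first table (40% Grade 2 only plus 20% Grade 3-4, assumed), the same calculation gives a stop in 15% of trials as written and 99.6% as reworded.

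**Pooling.** With 119 per group and no reference-arm cases, the Grade 3-4 limb needs 60/119 = 50.4% of the test arm.

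**The case against.** The strongest reply is that the bands problem needs an over-literal reading. If Grade 2 was meant as Grade 2 or higher, 60.1% fires the first limb. That may well be the intent. But the second limb names a range, Grades 3-4, which makes the single grade in the first limb look deliberate, and nothing elsewhere settles it. One phrase would.

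It is also fair that the trial can stop in other ways. The intolerance clause sits in the same sentence. Deaths and other SAEs go to the sponsor, usually within 24 hours (8.4.6). SUSARs are expedited (8.4.8), and 10.5.2 recognises termination by the investigator. A reader might infer that the trial could not be stopped at 60% or after a death; the documents do not support that. Only the numeric limbs have the gap.

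A reader might also go further and conclude that pooling is the main defect, because with equal groups ("with an equal number of participants per treatment group") test-arm Grade 2 events alone reach exactly 119/238 = 50.0% and so cannot exceed one half, and that per-arm counts are needed. This goes too far:

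- The impossibility is a boundary case. With 119 test and 118 reference participants dosed, 119/237 = 50.2% would fire, although every test participant would have to be affected. Under "The stratified block randomization will be adopted" the groups need not be equal at every interim moment.
- Dilution of a one-arm signal is general, but it follows from a blinded design. Section 6.6.3 says "Only the designated clinical site personnel responsible for drug distribution and administration could reach the randomization code" and, apart from SUSARs, does not permit unblinding. The unblinded statistician in 6.6.2 is described only as producing the schedule, so reviewing accumulating events by arm would be a new duty.
- Per-arm counts at 40 and 80 per group, with cumulative grades, would give false stops of about 26% at an assumed 40% Grade 2 plus 2% Grade 3-4, against about 3% for the present rule. They could also end the trial on the licensed reference product alone.

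The dilution is worth noting to the sponsor. Per-arm monitoring is a trade-off, and the documents do not show that it is required.

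**Conclusion.** The point holds for the grade bands. Read as written, item 1 lets 143 of 238 participants (60.1%), and at most 178 (74.8%), have drug-related events of Grade 2 to 4 without either numeric limb firing, and it leaves drug-related Grade 5 events out of both. This rests on reading Grade 2 as exactly Grade 2 and on the affected participants being different people.

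The practical risk is low. The 40 mg/0.8 mL strength is already approved (4.2), the judgement-based routes remain, and in a single-dose trial stopping helps only those not yet dosed. The documents give no dosing timetable, so the number who could be spared is unknown. All event rates used above are assumptions. The cited single-dose study had about 70% with any AE regardless of cause, mostly mild or moderate (2.2), which does not give a drug-related Grade 2 rate. No PK conclusion changes. This is a cheap improvement to a safety rule.

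**What to change.** In 10.5.1 and the synopsis, reword the numeric part of item 1 to:

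> more than half of the participants dosed experience drug-related AEs of Grade 2 or higher, or more than a quarter experience drug-related AEs of Grade 3 or higher, or any drug-related Grade 5 event occurs

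Keep the obvious-intolerance clause and items 2-4. Replace the not-applicable entry in 7.4 with a pointer to 10.5.1.

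The count stays pooled, so blinded staff can apply it and 6.6.3 is unchanged. The cost is wording in three places of the next amendment, with approval by or filing to the Ethics Committee (10.2). The SAP has no termination text to change, only its reference to the protocol version (SAP Section 1). Participants have no added procedures.

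The downside is more false stops if drug-related Grade 2 events are common: 6.65% against 2.88% at an assumed 40%, and under 1% at 35% or below. Those figures hold for counts at 80 and 160 dosed. Neither wording fixes a schedule or a minimum number, and when very few are dosed one or two events could trigger either, so the sponsor should know when it intends to count.

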10.5.2 Responsibilities of Sponsor/Investigators following Trial Termination

If the trial is prematurely terminated or suspended, the investigator should promptly inform the trial participants, should assure appropriate therapy and follow-up for the participants. In addition:

- [1] If the investigator terminates or suspends the trial without prior agreement of the sponsor, the investigator should inform the institution, the sponsor and IEC and should provide a detailed written explanation of the termination or suspension.
- [2] If the sponsor terminates or suspends the trial, the sponsor should promptly inform the investigators, the institution, IEC and the regulatory authority(ies), and provide a detailed written explanation of the termination or suspension.
- [3] If the IEC terminates or suspends its approval opinion of the trial, the investigator should inform the institution and the sponsor, and provide a detailed written

explanation of the termination or suspension.

11 GENERAL CONSIDERATIONS: RISK MANAGEMENT AND QUALITY ASSURANCE

11.1 Quality Tolerance Limits

Not Applicable.

11.2 Data Quality Assurance

The sponsor and investigator should establish their own quality assurance (QA) system and perform their duties respectively. They will follow the clinical trial protocol strictly and comply with the relevant SOPs to ensure the implementation of the quality control (QC) and quality assurance system.

The sponsor may perform inspection on different aspects of the clinical trial process, sample analysis, data, report and calculation process according to the actual requirement and progress of the trial and the verification results of the quality control personnel/ monitor.

11.2.1 Quality Assurance of Clinical Trial

The investigators will be trained of the clinical trial protocol to fully understand the protocol before the trial initiation. Quality control staff should inspect the clinical research facility for the essential conditions to ensure the requirements of the protocol can be met. Investigators will conduct the clinical operations conscientiously according to the SOPs of clinical research facility and the protocol requirements, and record the data accurately, timely, completely, and standardly. Quality control staff will audit the study procedures and the relevant original records. All trial documents will be collected after trial completion. Trial documents will be archived properly after quality control is finalized.

11.2.2 Quality Assurance of Bioanalytical Analysis

The bioanalytical laboratory will establish the quality assurance system, conduct independent and impartial quality audits including 100% audit on the process of data transference and calculation by quality control personnel in accordance with the sample analysis plan and SOPs and relevant guidance. The quality assurance personnel will audit the data and reports of the method validation, sample analysis process to ensure that the reports reflect bioanalytical analysis, SOPs followed and raw data.

11.2.3 Quality Assurance of Data Management

After the data entry into the eCRF, CRA 100% will check the (e)CRF data to determine whether it is complete, accurate and consistent with the original medical records. Queries should be promptly raised about data items that are questionable or inconsistent with the

original medical records. Clinical research coordinators (CRC) and investigators should have to answer the queries and verify / correct inconsistent data.

Data management staff will conduct logical inspection on the quality of data entry. Queries will be sent to investigators/CRC for verification and correction. The QC staff will verify the data management files and data in database. QA staff will conduct audit on data management documents and process.

Frontage Laboratories (Shanghai) Co., Ltd. will conduct the data management in accordance with the SOPs, GCP and relevant guidance and provide the data management reports.

11.2.4 Quality Assurance of Statistical Analysis

Statistical analysts will conduct the statistical analysis based on current regulations, guidelines, SOPs, and the SAP. Related personnel will conduct quality control on statistical analysis process and data processing result. QA will audit the documentations during statistical analysis and data processing to ensure that they are in accordance with relevant regulations, guidelines, SOPs, and the SAP.

11.3 Source Data

Source Data: All information in original records and certified copies of original records of clinical findings, observations, or other activities in a clinical trial necessary for the reconstruction and evaluation of the trial.

Source data are contained in source documents. Source data should be attributable, legible, contemporaneous, original, accurate, complete, consistent and durable. Changes to source data should be traceable, should not obscure the original entry, and should be explained.

